### 5.2 ASSUMPTIONS

#### 5.2.1 Test results

By assuming:

1. 50% of the participants will have active caries
2. On average there are 1 carious surface per patient with active caries
3. there is minimum of 2 naïve IP surfaces per pediatric patient which may be captured in BWR

Approximately, out of all patients included in the trial, 1.8% of all tooth surfaces are carious and 98.2% of all tooth surfaces are non-carious.

# Clinical Study Protocol 1

Based on previous iTero 5D study, we can assume that for NIRI, the sensitivity for early enamel lesions is 0.51 and specificity is 0.90.

The assumed test results can be summarized as:

	X-ray is the ground truth	
NIRI	Negative (no caries)	Positive (caries)
Negative (no caries)	88.38%	0.88%
Positive (caries)	9.82%	0.92%

## 5.2.2 Non- inferiority margin

Based on relevant literature and the results from previous trials, we can assume that the non-inferiority margin to be 5%.

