## 4. STUDY DESIGN

### 4.1 OVERVIEW OF STUDY DESIGN

This is a non-significant risk, single site, prospective study to be conducted in the department of pediatric dentistry of the Hadassah Medical Center, Faculty of Dental Medicine, Hebrew University of Jerusalem, Israel. Subject participation will require one visit during which consent, screening, enrollment, and imaging will be performed. An additional follow-up call to the Investigator will take place a month later to review patient records and capture any clinical information recorded since last trial visit if a treatment was planned.

Each subject will be assigned a unique ID number that will link to their data. De-identified data sets will be used for analysis.

Clinical and diagnostic methods to be used during this study are those that are routinely used in the diagnosis of caries in this site, which include bitewing radiographs (BWR). This standard of care is provided for all site’s patients, including the patients who don’t participate in this clinical study.

A standard set of BWR for subjects ages 4-9 years will be taken to include the complete dentition of the subjects. Any recent bilateral BWR which were obtained up to 14 days prior to study visit may be used. **No additional x-ray should be taken for the sole purpose of this trial.**

In addition to the routine clinical diagnostics, the subjects will be scanned using the 5D system. The investigator will capture a full arch scan of the maxillary arch and mandibular arch of each subject with the iTero Element 5D system. For each subject, the Investigator will grade carious lesions in the BWR and Element intra-oral scan according to ADA staging guidelines. The results will be documented using

# Clinical Study Protocol 1

Caries Evaluation Forms. The Investigator will assess and document the findings of each diagnostic test separately before reviewing the next test.

In cases where caries debridement indicated, carious lesion depth will be documented during and compared to NIRI and BWR images. **All treatment decisions will be made according to the standard of care in the clinic and no treatment will be conducted for the sole purpose of the study.**

The study will include an interim analysis to assess the iTero Element 5D system useability among the first 20 pediatric subjects. Based on the findings' evaluation, modifications in the study protocol for the remaining 50 subjects will be considered.

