## 5. STATISTICAL AND ANALYTICAL PLANS

### 5.1 HYPOTHESIS

The test results can be summarized in the following 2x2 table:

	X-ray is the ground truth	
NIRI	Negative (no caries)	Positive (caries)
Negative (no caries)	$P_{00}$	$P_{01}$
Positive (caries)	$P_{10}$	$P_{11}$

Where  $P_{ij}$  = the percentage of tooth surfaces under certain condition out of all included surfaces.

As we are taking X-ray as the ground truth,  $P_{01}$  is the percentage of surfaces that can be detected as caries by X-ray but not NIRI (NIRI missed detection rate),  $P_{10}$  is the percentage of surfaces that can be detected by NIRI, but not X-ray (NIRI over detection rate). By showing that NIRI over detection rate ( $P_{10}$ ) is not less than NIRI missed detection rate ( $P_{01}$ ) by non-inferiority margin of  $M$ , we can conclude that NIRI is non-inferior than X-ray in detecting caries. Thus,  $P_{10}-P_{01}$  provides a measure for assessment of a non-inferiority between two procedures.

Null Hypothesis:  $P_{10}-P_{01} \leq -M$

Alternate Hypothesis:  $P_{10}-P_{01} > -M$

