## 5.3 SAMPLE SIZE

Sample size can be calculated from the sample size equation for comparing paired nominal data by using McNemar’s test:

$$n = \frac{[z_{\alpha}\sqrt{p_{01} + p_{10}} + z_{\beta}\sqrt{p_{01} + p_{10} - (p_{01} - p_{10})^2}]^2}{(p_{10} - p_{01})^2}$$

Similar formulae can be obtained for the one-sided non-inferiority test by substituting  $z_{\alpha/2}$ ,  $p_{10}$  with  $z_{\alpha}$  and  $p_{10} + M$ :

$$n = \frac{[z_{\alpha}\sqrt{p_{01} + p_{10} + M} + z_{\beta}\sqrt{p_{01} + p_{10} + M - (p_{01} - p_{10} - M)^2}]^2}{(p_{10} + M - p_{01})^2}$$

where significance level  $\alpha = 0.05$ , power  $1 - \beta = 0.8$ , non-inferiority margin  $M = 5\%$ , assumed detection rate  $p_{01} = 0.22\%$ ,  $p_{10} = 2.46\%$

The minimum sample size required is 89 surfaces. Assuming the drop off rate to be 30%, an additional 39 surfaces will be recruited, so the total number of surfaces needed for the clinical trial is 128. assuming a minimum of 2 naïve IP surfaces per paediatric patient.

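### At the plan's stated 1.8% caries prevalence, the 5% all-surface margin means a device that detects no lesion still satisfies the primary non-inferiority hypothesis, and false positives are credited against missed lesions

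*Combined protocol and SAP*

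**What the plan says.** Section 5.1 takes the bitewing radiograph as ground truth and sets up a 2x2 table in which each cell is "the percentage of tooth surfaces under certain condition out of all included surfaces". P01 is the share positive on X-ray but missed by NIRI; P10 is the share positive on NIRI only. The null is P10 − P01 ≤ −M. On rejecting it, the section says "we can conclude that NIRI is non-inferior than X-ray in detecting caries". The primary endpoint in section 5.4.1 and the Study Summary makes the same claim.

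Section 5.2.2 fixes M: "we can assume that the non-inferiority margin to be 5"%. It cites literature and earlier trials but does not relate the margin to prevalence or to sensitivity.

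Section 5.2.1 states that "1.8% of all tooth surfaces are carious and 98.2% of all tooth surfaces are non-carious" and that "the sensitivity for early enamel lesions is 0.51 and specificity is 0.90". Its table follows from these figures: P00 = 88.38%, P01 = 0.88%, P10 = 9.82%, P11 = 0.92%. The same section assumes that half the children have active caries, with one carious surface each on average, and at least 2 "IP surfaces per pediatric patient which may be captured in BWR". Section 4.1 says "A standard set of BWR for subjects ages 4-9 years will be taken to include the complete dentition of the subjects".

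Section 5.3 concludes "The minimum sample size required is 89 surfaces", raised to 128 for drop-off, and enrols 70 children. Section 5.5 describes the test as comparing the false positive rate with the false negative rate at a margin of 0.05. It adds a two-sided McNemar test, a one-sided binomial test and kappa, none with a limit that must be met.

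**The concern.** A non-inferiority margin has to be smaller than the loss a useless device would produce. Here the margin is an absolute 5 points of all surfaces, whereas the most a device can lose by missing every lesion is the X-ray-positive prevalence. If that is 1.8%, the margin is nearly three times the largest possible deficit (5/1.8 = 2.8) and the test cannot protect against missed disease.

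The contrast also nets false positives against misses. With X-ray as ground truth, and with P10 labelled false positive in section 5.5, each overcall makes the device look better at detecting caries.

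At stake is the trial's single primary conclusion. It could be declared whatever share of the lesions NIRI misses.

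**Working it through.** **Inputs.** Prevalence 1.8%, sensitivity 0.51, specificity 0.90, 0.5 × 1 = 0.5 carious surfaces per child and a minimum of 2 surfaces per child (5.2.1); M = 5% (5.2.2); one-sided α = 0.05, power 0.80, p01 = 0.22%, p10 = 2.46% (5.3); 70 children.

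**The plan's own figure.** The non-inferiority formula in 5.3 with p01 = 0.22% and p10 = 2.46% gives n = 88.5, so 89. It reproduces.

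**The bound.** Let π be the X-ray-positive share:

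P10 − P01 = (1 − specificity)(1 − π) − (1 − sensitivity)π

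The minimum, at sensitivity 0 and specificity 1, is −π. At π = 1.8% that is −1.8 points, which is above −5. The null is attainable only if π ≥ 5%. With 0.5 carious surfaces per child, that means at most 0.5/0.05 = 10 analysed surfaces per child.

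**Offsetting, at π = 1.8% and specificity 0.90.** P10 = 0.982 × 0.10 = 9.82%.
- Sensitivity 0.51: P01 = 0.018 × 0.49 = 0.88%; difference +8.94 points.
- Sensitivity 0: P01 = 1.80%; difference +8.02 points.

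Putting P01 = 1.80% and P10 = 9.82% into the 5.3 formula gives n = 58.5, so 59. A device that detects no lesion reaches 80% power with fewer surfaces than the 89 planned.

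**Which denominator.** The stated 1.8% implies 0.5/0.018 = 27.8, about 28 surfaces per child, or 70 × 28 = 1,960 in all. The sizing minimum of 2 implies up to 0.5/2 = 25%.

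**Chance of passing.** These are exact multinomial probabilities at one-sided 0.05 with surfaces treated as independent. Section 5.5 says only that the test is asymptotic, so three variances are shown: Wald / planning formula / score. A Wald sample with no discordant surfaces is counted as a pass.

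At π = 1.8%:
- All-negative device: about 100% at 1,960 surfaces; 78/20/52% at 89; 80/33/59% at 128; 75/54/54% at 140. The last three pair 1.8% with counts taken from the 2-surface sizing.
- Sensitivity 0, specificity 0.90: 99/97/99% at 89.

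By analysed surfaces per child k, with n = 70k and π = 0.5/k:

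| k | π | Plan's device (0.51, 0.90) | Sensitivity 0, specificity 0.90 | All-negative |
|---|---|---|---|---|
| 2 | 25% | 6/4/6% | about 0% | about 0% |
| 3 | 16.7% | 59/49/57% | under 0.5% | about 0% |
| 4 | 12.5% | 95/92/95% | 12/9/11% | about 0% |
| 5 | 10% | over 99% | 53/45/52% | about 0% |
| 6 | 8.3% | about 100% | 89/84/88% | about 0% |
| 7 | 7.1% | about 100% | 99/98/99% | about 0% |
| 9 | 5.6% | about 100% | about 100% | 2/0/1% |
| 11 | 4.5% | about 100% | about 100% | 17/5/13% |
| 16 | 3.1% | about 100% | about 100% | 96/78/94% |
| 20 | 2.5% | about 100% | about 100% | about 100% |

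At k = 2 the plan's device has a true difference of 0.10 × 0.75 − 0.49 × 0.25 = −4.75 points, almost on the margin.

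**Do the other analyses block the claim?** Take sensitivity 0 and specificity 0.90 at π = 1.8%. Observed agreement is 0.8838 and chance agreement is 0.0982 × 0.018 + 0.9018 × 0.982 = 0.8873, so kappa = −0.03. That would look poor, but kappa has no pass limit. At 1,960 surfaces there would be about 192 false positives (0.0982 × 1,960) against 35 misses (0.018 × 1,960). The one-sided binomial test would therefore read as NIRI detecting more caries than X-ray.

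**The case against.** The strongest reply is that 1.8% is not a settled planning value. It does not follow from the plan's assumptions at 2 surfaces per child, which give 25%. The sizing inputs 0.22% and 2.46% are one quarter of the table's 0.88% and 9.82%, and the table values would give n = 48 in the same formula. At 2 or 3 surfaces per child the null is attainable and both useless devices almost never pass. This stands, and it limits the statement that the null cannot be true to prevalence below 5%. It does not rescue the plan. Two is described as a minimum and the radiographs cover the full dentition. At 2 per child the plan's own device fails about 94% of the time or more; from about 6 per child a device with sensitivity 0 and specificity 0.90 usually passes.

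Second, any McNemar-type contrast nets the two discordant cells. That is true, and reasonable when neither method is the reference. Here X-ray is declared the ground truth.

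Third, the pass rates at 89 to 140 surfaces vary widely with the variance used. About 20 points of the Wald 78% at 89 come from samples with no discordant surfaces (0.982^89 = 0.20), and clustering is ignored. This also stands for those rates, but the −1.8-point bound depends on none of it.

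Finally, care follows the clinic's standard, so the harm is to the claim and not to the children, and restating the margin on sensitivity would be an equally valid repair. Both points are fair; the second is left open below.

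**Conclusion.** The concern holds. On the plan's stated 1.8%, the primary null is false for every possible device, so the conclusion of non-inferiority in detecting caries is true by construction. At the matching 1,960 surfaces even an all-negative device passes about 100% of the time. This applies whenever fewer than 5% of analysed surfaces are X-ray positive, meaning more than 10 surfaces per child at 0.5 carious surfaces per child. The crediting of false positives against misses applies at any prevalence.

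The bound is arithmetic and needs only section 5.1's definitions and the prevalence. The pass rates also assume independent surfaces and the variance forms shown. Because the analysed surfaces are not fixed, the verdict turns on an unstated choice: at 2 per child the plan's own device almost certainly fails, and at about 6 or more a device that finds no lesion usually passes. The primary test needs to be changed before it is used.

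**What to change.** In 5.1, 5.2.2, 5.4.1, 5.5 and the Study Summary, stop drawing the non-inferiority conclusion from P10 − P01 with a 5% all-surface margin. Suggested text:

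> The primary results are the missed-lesion proportion P01/(P01+P11) and the specificity P00/(P00+P10) against BWR, each with a 95% confidence interval that allows for clustering of surfaces within child. P10 − P01 is reported as a descriptive contrast.

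In 5.2.1, state which surfaces per child are analysed and put the prevalence and the 2x2 table on that one denominator. In 5.3, use inputs that match the table and restate what 70 children can support.

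If the sponsor wants to keep a pass/fail verdict, it may set and justify limits on the two proportions. That is a separate design decision with its own sample-size calculation and possibly more children; the reporting change does not depend on it.

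**Cost.** The reporting change uses data already collected and needs only new protocol and SAP wording, but it does replace the primary endpoint and the basis of section 5.3. Without a limit, the primary becomes an estimate with no verdict. The headline is less favourable (assumed sensitivity 0.51) and precision is low: about 70 × 0.5 = 35 X-ray-positive surfaces give a 95% half-width for sensitivity of 1.96 × √(0.51 × 0.49/35) = 16.6 points before clustering (for 18/35, Wilson interval 0.36 to 0.67).

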## 5.3 SAMPLE SIZE

Sample size can be calculated from the sample size equation for comparing paired nominal data by using McNemar’s test:

$$n = \frac{[z_{\alpha}\sqrt{p_{01} + p_{10}} + z_{\beta}\sqrt{p_{01} + p_{10} - (p_{01} - p_{10})^2}]^2}{(p_{10} - p_{01})^2}$$

Similar formulae can be obtained for the one-sided non-inferiority test by substituting  $z_{\alpha/2}$ ,  $p_{10}$  with  $z_{\alpha}$  and  $p_{10} + M$ :

$$n = \frac{[z_{\alpha}\sqrt{p_{01} + p_{10} + M} + z_{\beta}\sqrt{p_{01} + p_{10} + M - (p_{01} - p_{10} - M)^2}]^2}{(p_{10} + M - p_{01})^2}$$

where significance level  $\alpha = 0.05$ , power  $1 - \beta = 0.8$ , non-inferiority margin  $M = 5\%$ , assumed detection rate  $p_{01} = 0.22\%$ ,  $p_{10} = 2.46\%$

The minimum sample size required is 89 surfaces. Assuming the drop off rate to be 30%, an additional 39 surfaces will be recruited, so the total number of surfaces needed for the clinical trial is 128. assuming a minimum of 2 naïve IP surfaces per paediatric patient.

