**The minimum required patient count and site count 70 patients in one trial site.**

## 5.4 STUDY MEASURES

### 5.4.1 Primary effectiveness endpoint measures

The iTero 5D will be non-inferior to BWR in detecting the existence of primary interproximal caries lesions above the gingiva.

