## 5.5 STATISTICAL ANALYSIS PLAN

Statistical tests will be performed to show comparison between iTero NIRI technology of the iTero Element 5D and bite-wing x-ray in detecting the existence of primary interproximal caries lesions above the gingiva

- Two-sided McNemar's Chi-square test to show if there is a statistically significant difference between the detection ability of the iTero NIRI technology of the iTero Element 5D and bite-wing x-ray
- Asymptotic Non-Inferiority test to show if the false positive (FP) rate ( $P_{10}$ ) is non-inferior than false negative (FN) rate ( $P_{01}$ ) with non-inferiority margin as 0.05, which means iTero NIRI technology of the iTero Element 5D is non-inferior than bite-wing x-ray in detecting primary interproximal caries
- One-sided binomial test to show if the false positive (FP) count ( $C_{10}$ ) is significantly higher than false negative (FN) count ( $C_{01}$ ), which indicates if iTero NIRI technology of the iTero Element 5D can detect more primary interproximal caries than bite-wing x-ray
- Kappa coefficient will be calculated to assess the agreement between two methods. (Moderate agreement (Kappa 0.41–0.60) is expected)

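### Section 5.3 puts the margin into the variance under the alternative, so 89 surfaces does not correspond to 80% power for the planned non-inferiority test

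*Combined protocol and SAP*

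**What the plan says.** Section 5.1 sets the null hypothesis P10 - P01 ≤ -M against P10 - P01 > -M and says that this difference "provides a measure for assessment of a non-inferiority between two procedures". Section 5.2.2 fixes M: "we can assume that the non-inferiority margin to be 5" percent. Section 5.5 plans an "Asymptotic Non-Inferiority test to show if the false positive (FP) rate" is non-inferior to the false negative rate, with margin 0.05; it does not name a variance estimator.

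Section 5.3 prints McNemar's superiority formula and then adapts it: "Similar formulae can be obtained for the one-sided non-inferiority test by substituting" z_α for z_α/2 and p10 + M for p10. With one-sided α = 0.05, power 0.8, p01 = 0.22% and p10 = 2.46%, it concludes: "The minimum sample size required is 89 surfaces". It then allows for losses ("Assuming the drop off rate to be 30%, an additional 39 surfaces will be recruited"), which gives 128 surfaces, and closes with "The minimum required patient count and site count 70 patients in one trial site".

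**The concern.** In Sections 5.1 and 5.5 the margin does one thing: it shifts the difference under test. In Section 5.3 it does two. It shifts the effect, which is right, and it also enlarges the assumed discordance, as though five more surfaces in every hundred were called positive by NIRI and negative by X-ray. Under the alternative, the variance of the paired difference depends only on the true discordance rates, so M has no place in that term.

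The size and the power are quoted as a pair, and the pair does not describe the planned test. The discrepancy is not a deliberate allowance for anything; Section 5.3 makes none, for example, for several surfaces coming from one child. The formula would also be reused if the sample size were recalculated, which is a realistic prospect: the rates in Sections 5.2.1 and 5.3 disagree, and Section 4.1 allows protocol changes to be considered after the first 20 subjects.

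**Working it through.** **Inputs.** From Section 5.3: p01 = 0.0022, p10 = 0.0246, one-sided α = 0.05 (z = 1.645), power 0.80 (z = 0.842). From Section 5.2.2: M = 0.05.

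**1. Reproduce the plan's figure.** The printed formula is

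n = [z_α √(p01 + p10 + M) + z_β √(p01 + p10 + M - (p01 - p10 - M)²)]² / (p10 + M - p01)²

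- Effect: 0.0246 + 0.05 - 0.0022 = 0.0724
- Null term: 0.0022 + 0.0246 + 0.05 = 0.0768
- Alternative term: 0.0768 - 0.0724² = 0.0716
- n = [1.645 √0.0768 + 0.842 √0.0716]² / 0.0724² = 88.47, so 89
- Losses: 89 / 0.7 = 127.1, so 128

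The plan's numbers are reproduced exactly, so the source of the 89 is not in doubt.

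**2. Variance under the alternative.** From the stated rates it is

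p01 + p10 - (p10 - p01)² = 0.0268 - 0.0224² = 0.0263

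The printed term, 0.0716, is about 2.7 times as large (0.0716 / 0.0263).

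**3. Variance under the null.** This depends on the test.

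- *Score test.* The restricted maximum-likelihood rates at P10 - P01 = -0.05 are p01 = 6.19% and p10 = 1.19%. The variance is 0.0619 + 0.0119 - 0.05² = 0.0713, close to the plan's 0.0768.
- *Wald test.* The same variance, 0.0263, serves in both terms.

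**4. Corrected sizes for 80% power, one-sided 0.05.**

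- Score: [1.645 √0.0713 + 0.842 √0.0263]² / 0.0724² = 63.2, so 64
- Wald: (1.645 + 0.842)² × 0.0263 / 0.0724² = 31.0, so 32
- Plan's null term kept, alternative term alone corrected: [1.645 √0.0768 + 0.842 √0.0263]² / 0.0724² = 66.9

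The last line locates the error. Correcting the alternative term alone takes 88.5 down to 66.9; replacing the null term as well takes it only from 66.9 to 63.2.

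**5. Power at 89 independent surfaces under the Section 5.3 rates.**

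| Test | Normal approximation | Exact enumeration |
|---|---|---|
| Score | 93.4% | 99.3% |
| Wald | 99.5% | 99.9% |

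**6. The same comparison with the Section 5.2.1 cells** (p01 = 0.88%, p10 = 9.82%; effect 0.1394). The alternative variance is 0.1070 - 0.0894² = 0.0990, against 0.1570 - 0.1394² = 0.1376 in the printed form. The restricted null variance is 0.1454.

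| Inputs | Printed formula | Score | Wald |
|---|---|---|---|
| Section 5.3 | 88.5 (89) | 63.2 (64) | 31.0 (32) |
| Section 5.2.1 | 47.8 (48) | 40.9 (41) | 31.5 (32) |

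**7. Reliability of the approximations.** At 89 surfaces the expected number of discordant surfaces is 89 × 0.0268 = 2.4. Normal-theory sizes are rough with so few: the score formula's 64 surfaces have exact power of 92.6%, not 80%. The Wald test also fails to hold its level here. Its exact type I error at 89 surfaces was 0.067 and 0.172 in two null cases tried (p10 = 2.46% with p01 = 7.46%, and p10 = 0 with p01 = 5%).

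**The case against.** The strongest reply is that the error is harmless: it overstates the number needed, the plan enrols more than that number, and the repair changes neither the test nor the conduct of the trial. This stands as far as it goes. Under the Section 5.3 rates the error does not leave the study short of power, and a reader who inferred that it does would be wrong. What remains is that the documents state a size and a power that do not belong together.

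A second reply is that the variance may legitimately rise with M. For the null term that is correct. If P10 - P01 equals -5%, total discordance is at least 5%, and a score test uses 7.13% against the plan's 7.68%. It would therefore be too strong to say that M is wrong wherever it appears under a square root. The reply does not reach the alternative term.

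A third reply is that Section 5.5 leaves the variance estimator open, so the documents fix no single correct size. That also stands: 64 and 32 are sizes for two standard choices, and preferring the score test is a judgement. Neither choice gives 89. Since both come from normal approximations that are weak here, neither should be adopted as a replacement target.

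**Conclusion.** The point holds as a definite but conservative error in the sample-size justification. The variance under the alternative should be 2.63% on the stated rates, and the formula uses 7.16%. The 80%-power size by normal theory is about 64 surfaces (score) or 32 (Wald), not 89, and exact power at 89 is about 99%. With the Section 5.2.1 cells the gap is smaller: 48 printed, against 41 or 32.

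These figures assume independent surfaces, one-sided α = 0.05, M = 5%, and the rates shown. A reader might infer from them that the trial is oversized and could enrol fewer children. The documents do not support that. The surplus disappears or changes with the inputs, and the Section 5.3 rates are about a quarter of those in Section 5.2.1 (0.22% against 0.88%; 2.46% against 9.82%). It also ignores clustering, although Section 5.2.1 assumes that "there is minimum of 2 naïve IP surfaces per pediatric patient", so that each child contributes more than one surface.

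**What to change.** Rewrite the sample-size paragraph of Section 5.3 and one line of Section 5.5:

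1. In Section 5.5, name the non-inferiority test and its variance estimator, for example a score test with restricted maximum-likelihood null variance.
2. In Section 5.3, keep M in the effect, use the null variance that belongs to the named test, and use p01 + p10 - (p10 - p01)² for the alternative.
3. Use one set of discordance rates, reconciled between Sections 5.2.1 and 5.3.
4. Replace the pairing of 89 surfaces with 80% power by the power that the planned 70 children give. Obtain it by exact calculation or simulation, because few discordant surfaces are expected, and allow for surfaces clustered within a child under a stated range of within-child correlation.

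The cost is a text change and a short simulation. The formula correction itself calls for no extra children. Whether 70 is enough once the inputs are reconciled and clustering is allowed for is what step 4 has to show.

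### The sample-size inputs in section 5.3 contradict section 5.2.1, and the power of 70 children depends on a surface count per child that the plan never states

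*Combined protocol and SAP*

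**What the plan says.** Section 5.2.1 assumes that half the children have active caries and states: "On average there are 1 carious surface per patient with active caries". It also assumes at least 2 naïve interproximal surfaces per child on the bitewings. From this it concludes that "1.8% of all tooth surfaces are carious and 98.2% of all tooth surfaces are non-carious". With sensitivity 0.51 and specificity 0.90, its 2x2 table gives P01 = 0.88% and P10 = 9.82%.

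Section 5.3 applies a McNemar-type non-inferiority formula with one-sided alpha 0.05, power 0.80 and margin 5%, but enters p01 = 0.22% and p10 = 2.46%. The result is "The minimum sample size required is 89 surfaces". After a 30% allowance the text reads "so the total number of surfaces needed for the clinical trial is 128. assuming a minimum of 2" surfaces per child. The line that closes the section is "The minimum required patient count and site count 70 patients in one trial site".

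Three other places bear on this:

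- Section 5.1 defines each Pij as "the percentage of tooth surfaces under certain condition out of all included surfaces".
- Section 4.1 says "A standard set of BWR for subjects ages 4-9 years will be taken to include the complete dentition of the subjects".
- Section 5.5 adds, for NIRI against bitewings, "Moderate agreement (Kappa 0.41–0.60) is expected".

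**The concern.** The rates entered in 5.3 are not the rates derived in 5.2.1, and no reason is given. The plan also uses two surface counts for one denominator: about 28 per child behind the prevalence, and 2 per child when surfaces become patients. Because Pij is a share of all included surfaces, the two counts must agree. With carious surfaces fixed at 0.5 per child on average, fewer included surfaces means higher prevalence, higher P01, and an expected difference closer to the margin.

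At stake is the stated 80% power of the only primary test. A reader cannot tell whether 70 children give almost no power or nearly complete power.

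**Working it through.** **Inputs.** Alpha 0.05 one-sided, power 0.80, M = 0.05 (sections 5.2.2 and 5.3); sensitivity 0.51, specificity 0.90, 50% of children affected with 1 carious surface each (5.2.1); 30% loss, a minimum of 2 surfaces per child, 70 children (5.3).

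**Formula (5.3).** With s = p01 + p10 + M and d = p10 + M − p01:

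n = [1.645·√s + 0.8416·√(s − d²)]² / d²

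Rearranged, power = Φ{(√n·d − 1.645·√s) / √(s − d²)}.

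**1. The plan's figure reproduces from the rates in 5.3.** s = 0.0768, d = 0.0724, n = 88.5, so 89. Then 89/0.7 = 127.1, so 128.

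**2. The rates in 5.2.1 give a different figure.** The table follows from its own inputs: 0.018 × 0.49 = 0.88% and 0.982 × 0.10 = 9.82%. Then s = 0.157, d = 0.1394, n = 47.8, so 48. Power at 89 surfaces is 96%.

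**3. The rates in 5.3 are quartered and fit no scenario.** 0.88/4 = 0.22 and 9.82/4 = 2.455. At sensitivity 0.51, p01 = 0.22% needs a prevalence of 0.0022/0.49 = 0.45%. At specificity 0.90, p10 = 2.46% needs 1 − 0.0246/0.10 = 75.4%. No prevalence gives both.

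**4. There are two surface counts.** Carious surfaces per child = 0.5 × 1 = 0.5. A prevalence of 1.8% implies 0.5/0.018 = 27.8 surfaces per child. Exactly 2 per child implies 0.5/2 = 25%.

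**5. The patient count is not derived.** 128/2 = 64, not 70.

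**6. Power by mean surfaces per child, k.** Prevalence = 0.5/k, p01 = 0.49 × prevalence, p10 = 0.10 × (1 − prevalence). Surfaces are treated as independent and all surfaces are analysed: n = 70k, or 49k after 30% loss.

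| k | Prevalence | p01 | p10 | Power, 70k | Power, 49k | Expected kappa |
|---|---|---|---|---|---|---|
| 2 | 25% | 12.25% | 7.50% | 6% | 6% | 0.44 |
| 3 | 16.7% | 8.17% | 8.33% | 49% | 38% | 0.41 |
| 4 | 12.5% | 6.13% | 8.75% | 89% | 78% | 0.38 |
| 5 | 10% | 4.90% | 9.00% | 99% | 95% | 0.35 |
| 6 | 8.3% | 4.08% | 9.17% | >99% | 99% | 0.32 |
| 28 | 1.8% | 0.88% | 9.82% | >99% | >99% | 0.12 |

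At k = 2 the expected p10 − p01 is −4.75%, only 0.25 points inside the −5% margin, so power is barely above alpha. Power reaches 80% at k of about 3.7 (70k) or 4.1 (49k).

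**7. Clustering, as an assumption.** The documents give no intraclass correlation. Dividing 70k by 1 + (k − 1)·ICC, for ICC 0.1 to 0.2, gives power of 43% to 39% at k = 3, 81% to 74% at k = 4, and 99% to 97% at k = 6.

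**8. Kappa (minor).** The 5.2.1 table gives observed agreement 0.893 and chance agreement 0.878, so kappa = 0.12. On these inputs the expected range of 0.41 to 0.60 is met only at about 2 to 3 surfaces per child (0.438 at 2; 0.408 at 3, just at its lower edge).

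**The case against.** The strongest reply is that nothing harmful follows. 89, 128 and 80% power do follow from the rates typed into 5.3. Those rates ask for more surfaces than the table needs, and 70 exceeds 64. The figure 2 is called a minimum, so it may be a cautious floor for recruitment beside a larger mean; bitewings that cover the complete dentition make a mean of exactly 2 unlikely. It is fair that the quartering alone is conservative and that 2 is a worst case. But that comfort holds only if the mean is well above 4, and the plan does not say so. A floor used for recruitment cannot be combined with a prevalence that assumes 28.

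Other points stand in part:

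- **Sensitivity.** The 0.51 is quoted for early enamel lesions only. With an assumed 0.60 to 0.80, power at 2 surfaces per child (140 surfaces) would be 15% to 69%. But 5.2.1 itself applies 0.51 to every carious surface.
- **Test.** Section 5.5 names an asymptotic test without a formula. If it is a Wald test of the paired difference, 80% power needs about 3.4 surfaces per child (3.8 after loss) and power at 3 is 58%. The picture is unchanged.
- **Loss.** Section 4.4 allows withdrawn subjects to be replaced, which softens the 30%-loss column. The no-loss column is unaffected.
- **Kappa.** It is an expectation, not a success criterion, so the mismatch is secondary.

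**Conclusion.** The concern holds and should be corrected before NIRI and bitewing results are compared. The rates in 5.3 contradict 5.2.1 by a factor of 4, the prevalence and the patient conversion rest on about 28 and 2 surfaces per child, and 70 is not derived. No single set of the plan's assumptions yields 89, 128, 70 and 80% power together.

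The direction of the error depends on the unstated count. At about 28 surfaces per child the study has ample power; at 2 to 3, power is roughly 6% to 49%. These figures rest on the plan's formula, its sensitivity and specificity, 0.5 carious surfaces per child, and independence of surfaces within a child. Clustering would lower them.

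**What to change.** - In 5.2.1, state one mean number of evaluable interproximal surfaces per child, and use it for both the prevalence and the surface-to-patient conversion.
- From it, with sensitivity 0.51 and specificity 0.90, derive p01, p10, the required surfaces, power and expected kappa. Replace 0.22%, 2.46%, 89, 128 and the kappa range with the results.
- Keep 70 children, say how 70 was reached, and give its power before and after 30% loss.
- State that the formula treats surfaces within a child as independent.
- If no figure is available, the surface count can be taken from the usability review of the first 20 children, without comparing NIRI with bitewings.

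The cost is a text change, with no extra enrolment. The stated power will look worse if only 2 to 3 surfaces per child are evaluable; with about 4 or more it stays near or above 80% under independence.
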